**Intervention Groups and Duration:**

[figure not shown]
All participants will receive 2 doses of Fabrazyme® first, administered as an IV infusion at a dose of 1.0 mg/kg of body weight with 14 days between doses. After that, all participants will receive AGA BETA BS, administered at dose of 1 mg/kg of body weight, infused every 2 weeks as an IV infusion, for up to 54 weeks (27 infusions).

1. Non-investigational prophylactic pretreatment with antihistamine will be administered at the Investigator's discretion to avoid infusion-associated reactions during the study, except during the first 2 infusions in period 2 in which administration will be compulsory. The antihistamine will be loratadine 10 mg, 1 to 2 hours before infusion, oral route. Furthermore, patients must remain in observation at the study center for at least 1 hour after each infusion during the first four AGA BETA BS infusions. In subsequent infusions, the center staff will contact each patient within 24 hours after infusion to check their clinical condition.

**Data Monitoring/Other Committee:** No

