## 4.0 STUDY DESIGN

### 4.1 Overall Design

This is a Phase III, prospective, multicenter, open-label, single-group, baseline-controlled, switch over clinical trial to evaluate the efficacy and safety of AGA BETA BS treatment in patients with FD already treated and previously stabilized with Fabrazyme.

The planned clinical trial aims to establish the equivalence of AGA BETA BS to Fabrazyme®.

A schema of the trial design is shown in Section 1.2.

Approximately 20 participants aged  $\geq 16$  years and  $\leq 60$  years with FD who are receiving Fabrazyme® for at least 6 months, have received at least 80% of the prescribed dose during the last 3 months, and with disease status considered clinically stabilized at the Investigators' discretion, will be enrolled in this trial.

Screening will be performed between 35 to 42 days prior to the first dose of study experimental treatment. After all protocol-required safety laboratory tests (refer to Section 10.4), eligible participants will enter the study that comprises 2 periods:

1. Lead-in period: all participants will receive 2 intravenous (IV) infusions of Fabrazyme®, provided by Biosidus, at a dose of 1 mg/kg of body mass, with 14 days between doses. The participant's baseline status will be assessed at the end of this period.
2. Treatment period: all participants will switch treatment to AGA BETA BS, administered at dose of 1 mg/kg of body mass, infused every 2 weeks as an IV infusion, for up to 54 weeks. Participants will receive a total of 27 infusions.

During each infusion, participants will be monitored constantly to ensure prompt treatment for eventual IARs that could be presented. Prophylactic pretreatment with antihistamines to avoid IARs will be at the Investigator's discretion during the study, except during the first 2 infusions in period 2 in which administration will be compulsory. In addition, patients must remain in observation at the study center for at least 1 hour after each infusion during the first four AGA BETA BS infusions. In subsequent infusions, the center staff will contact each patient within 24 hours after infusion to check their clinical condition (refer to Section 6.8).

Preferably, all infusions should be performed at the study sites. The population to be evaluated in this study is already being treated with Fabrazyme® and, in accordance with the clinical

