practice for patients receiving ERT, in most cases it is at home. To allow full participation in the study and to avoid a significant number of drop-outs, infusions may be administered at the participant's home after 4 infusions of AGA BETA BS at the site, at the discretion of the Investigator. Before making this decision, the Investigator must ensure that AGA BETA BS infusions can be safely, effectively and reliably administered at the participant's home. Among other requirements that the Investigator may consider, it is recommended that the participant meet at least the following main criteria:

- The participant is considered medically stable. A comprehensive assessment must be completed prior to deciding on transfer of therapy.
- The participant must have a proven pattern of well-tolerated infusions.
- The participant must have a history of compliance with the prescribed infusion schedule.

The study site personnel are required to contact the participant by phone call or message texts in 2 situations: (1) before each study appointment or visit, for all participants, and (2) within 24 hours after infusion from the fifth infusion of AGA BETA BS. Refer to Section 8.1.5 for detailed information.

The trial will last approximately 60 weeks (including a 5-week Lead-in period and a treatment period of up to 54 weeks) and will have 5 key medical visits. Participants will undergo visits and trial procedures as shown in Schedule of Activities (SoA) in Section 1.3.

Refer to Section 10.3.5 for details on informed consent and to Section 10.3.11 for a definition of study start and a definition of “enrollment”.

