## **6.8 Concomitant Therapy**

Any medication or vaccine (including over-the-counter or prescription medicines, recreational drugs, vitamins, and/or herbal supplements) that the participant is receiving at the time of enrollment or receives during the study must be recorded on the eCRF along with:

- Reason for use
- Dates of administration including start and end dates
- Dosage information including dose and frequency
- For vaccines (if applicable) include brand name and manufacturer (plus lot number, if available)

The participant will receive a diary to record any concomitant medication that he or she may use during the study. The delivery of the diary to the participant and its collection for evaluation is described in the SoA (Section 1.3). The participant must be instructed to take the diary with them to each medical visit and each infusion appointment for evaluation. All information collected in the diary must be recorded on the eCRF.

Any questions regarding concomitant or prior therapy should be raised to the Sponsor's emergency contact.

Non-investigational pretreatment with antihistamine will be administered to avoid IARs at the Investigator's discretion in period 1 but will be compulsory during the first 2 infusions in period 2. The antihistamine pretreatment will also be at Investigator's discretion on the following infusions. This medication will be provided by Biosidus to study sites and is described in [Table 5](#). When used, the antihistamine medication must be recorded as concomitant medication.

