### **8.1.5 Phone Calls or Text Messages**

The study site personnel will contact the participant by phone call or text message in 2 situations:

- For all participants, 24 to 48 hours before each study appointment or visit to check on symptoms compatible with COVID-19 or other infection. If suspected or positive infection, to receive the infusions the participants must wait for clinical recovery, ie, 48 hours being afebrile. Refer to Section [7.1.1](#).
- From the fifth infusion of AGA BETA BS onwards, within 24 hours after infusion to check the patient's clinical condition.

All contact attempts, whether calls or text messages, must be recorded in the source documents.

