## 17.1 Adverse Events

All Adverse Events (AE) recorded in study will be coded using the MedDRA central coding dictionary version 25.1.

An AE will be defined as a treatment-emergent adverse event (TEAE) if they start on or after the date of the first dose of AGA BETA BS and would be counted only under treatment period and Non-TEAEs under Lead-in period in treatment period.

See [Appendix 1](#) for handling of partial dates for AEs. In the case where it is not possible to define an AE as treatment emergent or not, the AE will be classified by the worst case, i.e. treatment emergent.

Adverse events collected during the trial will be summarized by treatment groups and Period based on SAF population. Adverse events Listings will be presented for ITT population.

The number of AE and the number and percentage of patients experiencing AE will be summarized by severity and relationship to the Fabrazyme® and AGA BETA BS.

SAEs and AEs leading to premature study discontinuation will be summarized.

Listings will be provided for AEs based on severity and relationship to study medication.

Listings will be provided for AEs, SAE and AEs leading to discontinuation from study.

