### 17.1.5 Infusion Associated reaction(IAR)

An AE related to the infusion of study drug is referred to as an Infusion associated reaction (IAR) and will be identified by patients recording is the event an Infusion-Associated Reaction (IAR)? as “Yes”. ADR will be summarized by SOC/ PT and presented as listing.

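### Infusion-reaction follow-up and premedication differ by design between lead-in and treatment, and the SAP sets the two periods side by side without a per-infusion denominator

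*SAP*

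**What the plan says.** **Follow-up after infusion.** Protocol 4.1 says that "patients must remain in observation at the study center for at least 1 hour after each infusion during the first four AGA BETA BS infusions". Protocol 8.1.5 then has the site contact the participant "From the fifth infusion of AGA BETA BS onwards, within 24 hours after infusion". Neither measure is stated for the two lead-in Fabrazyme infusions.

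**Premedication.** Protocol 6.8 leaves antihistamine to the Investigator's "discretion in period 1 but will be compulsory during the first 2 infusions in period 2", and again to the Investigator's "discretion on the following infusions". Other premedication, such as antipyretics or corticosteroids, is discretionary throughout. All of it is recorded as concomitant medication.

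**Setting.** Under Protocol 4.1, infusions may be given at the participant's "home after 4 infusions of AGA BETA BS at the site".

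**Shared by both periods.** Protocol 4.1 has participants monitored constantly during every infusion. The AE diary is reviewed at every appointment (schedule of activities; Protocol 8.4.1). Open-ended questioning is the preferred way to elicit AEs (Protocol 8.4.2).

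**Analysis.** SAP 17.1 states: "Adverse events collected during the trial will be summarized by treatment groups and Period based on SAF population". SAP 17.1.1 adds an overview for both periods, IARs included, as number of events and n (%). SAP 17.1.5 defines the term without an onset window ("An AE related to the infusion of study drug is referred to as an Infusion associated reaction (IAR") and plans a summary by SOC and PT plus a listing; it names neither product nor period. SAP 17 rules out formal safety comparisons. SAP 14 tabulates the number of administrations per period but does not link it to the AE tables.

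**The concern.** The listed safety objective is to characterise AGA BETA BS alone. The protocol's rationale, however, presents the trial as comparative and aims to assess similarity to the innovator in safety as well as efficacy. With one arm, the lead-in is the only on-study Fabrazyme record, so readers will set its column against the AGA BETA BS column.

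Three things differ between those columns apart from the product:

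- **Post-infusion capture.** IARs have no onset window, so a reaction after the infusion ends counts. It is actively looked for only after AGA BETA BS.
- **Premedication.** It is compulsory only at the first two infusions after the switch.
- **Exposure.** One column covers 2 infusions and the other 27.

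More active follow-up would tend to raise the AGA BETA BS count, and compulsory antihistamine would tend to lower it. A difference between the columns could come from method or exposure alone, and a real difference could be hidden. Nothing in the SAP tells the reader so.

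**Working it through.** **1. The plan's own count.** Infusion k of AGA BETA BS falls on Day 1 + 14(k - 1), and the Day 379 final visit has no infusion. For k = 27 this is Day 365, and the next slot would be Day 379. That reproduces the 27 infusions stated in Protocol 4.1. Infusion 5, where the follow-up method changes, falls on Day 57.

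**2. Conditions side by side** (Protocol 4.1, 6.8 and 8.1.5).

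| Band | Infusions | Monitored during infusion | Required post-infusion check | Antihistamine | Home infusion possible |
|---|---|---|---|---|---|
| Fabrazyme 1-2 | 2 | yes | none | discretionary | no |
| AGA BETA BS 1-2 | 2 | yes | 1-hour observation | compulsory | no |
| AGA BETA BS 3-4 | 2 | yes | 1-hour observation | discretionary | no |
| AGA BETA BS 5-27 | 23 | yes | contact within 24 hours | discretionary | yes |

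**3. Coverage.**
- Required post-infusion check: 0/2 versus (4 + 23)/27 = 27/27. Observation accounts for 4/27 = 14.8% and contact for 23/27 = 85.2%.
- Compulsory antihistamine: 0/2 versus 2/27 = 7.4%.
- With 20 patients, the maximum is 20 × 2 = 40 Fabrazyme and 20 × 27 = 540 AGA BETA BS infusions.

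**4. Exposure alone.** Suppose the risk per infusion, p, is the same for both products, detection is equal and infusions are independent. The share of patients with at least one IAR is 1 - (1 - p)^n, with n = 2 or 27. The documents give no p, so the values are assumed.

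| Assumed p | Lead-in, n = 2 | Treatment, n = 27 |
|---|---|---|
| 0.5% | 1.0% | 12.7% |
| 1% | 2.0% | 23.8% |
| 2% | 4.0% | 42.0% |
| 5% | 9.8% | 75.0% |

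An n (%) display therefore differs greatly between two identical products.

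**5. Method alone.** Let s be the share of reactions detected in lead-in relative to treatment, and r the risk ratio from compulsory antihistamine at AGA BETA BS infusions 1-2. Treat observation and 24-hour contact as equally sensitive. With equal true risk, the apparent AGA BETA BS to Fabrazyme ratio per infusion is:
- over all 27 infusions: (2r + 25)/(27s)
- over infusions 1-2: r/s

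The documents give neither s nor r. The assumed ranges are s = 0.6 to 1.0 and r = 0.5 to 1.0.
- All 27, lowest (r = 0.5, s = 1): 26/27 = 0.96. Highest (r = 1, s = 0.6): 27/(27 × 0.6) = 1.67.
- Infusions 1-2, lowest: 0.5/1 = 0.50. Highest: 1/0.6 = 1.67.

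Both ranges include 1, so the direction is not fixed. A per-infusion denominator removes the exposure problem in step 4 but not the method problem here.

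**6. What can be contrasted.** Fabrazyme 1-2 and AGA BETA BS 3-4 both have discretionary antihistamine, and both are monitored during infusion. For reactions that start during the infusion, neither the post-infusion check nor the compulsory antihistamine enters. This is the nearest to a like-for-like contrast that the design offers.

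**The case against.** The strongest reply is that little rests on these columns. The safety objective concerns one product, no formal comparison is planned, and no decision rule uses the period display. Capture common to both periods is substantial: a late lead-in reaction can still be entered in the diary and reported at the next appointment. The coverage shares in step 3 describe conditions and do not measure bias, and the ranges in step 5 rest wholly on assumed inputs. Premedication and IARs are in any case to be listed by patient. All of this stands, and it keeps the point to description and labelling.

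Three stronger readings are tempting, and the documents do not support them.

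- A reader might infer that IAR rates must differ, or that the AGA BETA BS column is biased in a known direction. The documents fix the conditions, but they give neither the detection loss nor the antihistamine effect, and the two would act in opposite directions.
- A reader might infer that the SAP will show misleading steps at infusion 3 or infusion 5, or trends by time on drug. It plans no AE or IAR table by infusion number or time on drug.
- A reader might want IARs split by antihistamine given or not. Where use is discretionary, patients prone to reactions are likelier to receive it, so the split is confounded by indication. Where use is compulsory, the untreated cell could hold only deviations.

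The reply does not dispose of the core. Two columns collected under different rules, with a 2-to-27 exposure imbalance, are shown together without a denominator or a caveat, in a trial whose rationale includes similarity in safety.

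**Conclusion.** The concern holds in a limited form. Ascertainment and premedication differ by design between the periods: a required post-infusion check for 0 of 2 versus 27 of 27 infusions, and compulsory loratadine for 0 of 2 versus 2 of 27. Exposure differs at 2 versus 27 infusions, with no per-infusion denominator in the AE and IAR summaries. The period columns therefore cannot be read as a product comparison.

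The design facts and counts come straight from the protocol. The size of any distortion cannot be derived from the documents; the figures in steps 4 and 5 are illustrations under stated assumptions. Exposure is the difference whose effect on n (%) is plainest, since it arises even with identical products followed identically. This is a reporting weakness that is cheap to repair. It does not affect the primary efficacy analysis.

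**What to change.** In SAP 17.1.5, add one descriptive table of IARs per infusion administered, in four bands: Fabrazyme 1-2, AGA BETA BS 1-2, AGA BETA BS 3-4 and AGA BETA BS 5-27.

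- In each band, report the proportion of infusions given with antihistamine or other premedication, as description only. Do not split the IARs by premedication.
- Show IARs with onset during the infusion separately from later onsets wherever onset time is recorded. Give IARs of unknown onset time their own row. Same-day onset should not stand in for onset during infusion, because it would bring in reactions found during the 1-hour observation.
- Footnote the period columns in SAP 17.1 and 17.1.1: post-infusion follow-up, premedication, possible home infusion after infusion 4 and number of infusions all differ by period.

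The cost is SAP wording, one table and a little programming. The denominators and premedication records are already collected. Cells will be sparse, with at most about 40 Fabrazyme infusions from 20 patients, so the table describes and cannot test. No clinical procedure is altered.

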### 17.1.1 All AEs

An overview of AE summary will be provided for both Lead-in period and Treatment period with the No. of events and n (%).

Following points will be considered in overview of AE

At least one

- AE
- Treatment related AE
- Severe AE
- Serious AE
- AE leading to discontinuation of study medication
- AE leading to Death
- Infusion Associated reactions
- Serious events
- AEs with maximum severity
- Relationship to Treatment (Study Medication)
- Action taken with AGA BETA BS and Fabrazyme®
- AEs by Outcome

Incidence of AEs will be presented by System Organ class (SOC) and Preferred Term (PT) and broken down further by maximum severity and relationship to study medication (AGA BETA BS) for Treatment period.

---

Document: \\needc-vnasc01\Biosdata\Biosidus\Agalsidase Beta\YZAA1358\Biostatistics\Documentation\SAP

Author: [name]

Version Number: V1.0

Version Date: 08May2025

Template No.: CS\_TP\_BS016 Revision 7

Reference: CS\_WI\_BS005

Effective Date: 01Nov2021

The number of patients with incidence of AE in two groups will be summarized and presented with frequency and percentage n (%) for Treatment period.

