#### **9.2.5 Safety Analyses**

For laboratory parameters and other safety variables, both the actual value and the change from the baseline value will be summarized at each visit using the n, mean, SD, median, minimum value, and maximum value.

Change from baseline, frequency counts and percentage as applicable after 14, 26, and 54 weeks of treatment will be summarized for laboratory parameters including hematology, clinical chemistry, blood urea nitrogen, eGFR, urine albumin-creatinine ratio, electrolytes, and phosphate, from blood and urine samples collected.

Change from baseline analyses after 26 weeks and 54 weeks of treatment will be summarized for cardiac function tests including electrocardiogram and bidimensional echocardiogram exams.

For the immunogenicity variable, anti-AGA levels from blood samples will be analyzed at baseline, after 14, 26, and 54 weeks of treatment, and will be summarized by counts and percentages.

Physical assessments, AEs and IARs will be summarized by frequency counts and percentage.

Duration of exposure to investigational product and number of injections will be summarized descriptively by treatment group.

For all safety and immunogenicity variables, no formal statistical analysis will be performed.

All safety analyses will be performed on the Safety Analysis Set.

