### 3 STUDY DESIGN

#### 3.1 General Description

BIO-AGA-Fase III-001 is a Phase III, prospective, multicenter, open-label, single-group, baseline-controlled, switch over clinical trial to evaluate the efficacy and safety of AGA BETA BS in patients with FD already treated and previously stabilized with Fabrazyme®.

The study will be conducted in 2 parts: a 5-week Lead-in period (period 1) and 54-week treatment period (period 2).

Details regarding Lead-in period and treatment period are provided below:

1. Lead-in period: all participants will receive 2 intravenous (IV) infusions of Fabrazyme®, provided by Biosidus, at a dose of 1 mg/kg of body mass, with 14 days between doses. The participant's baseline status will be assessed at the end of this period.
2. Treatment period: all participants will switch treatment to AGA BETA BS, administered at dose of 1 mg/kg of body mass, infused every 2 weeks as an IV infusion, for up to 54 weeks. Participants will receive a total of 27 infusions.

The design of this study is based on that used for the only biosimilar approved in an ICH member country (Japan). In both, a "patient's own historical control" is used as a control, in which the efficacy of AGA BETA BS is measured by comparing the value of the surrogate marker (Lyso-Gb3) at baseline - after at least 6 months of treatment with Fabrazyme® - compared to the value at 6 and 12 months of treatment with AGA BETA BS. This will be a paired comparison that maximizes the ability to detect variations in treatment efficacy.

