## 14 STUDY MEDICATION EXPOSURE

Exposure to study Fabrazyme/ AGA BETA BS in weeks will be presented and summarized for the ITT population for Lead-in Period and Treatment Period respectively.

Duration of exposure (in weeks), no. of IP administrations, Number of patients exposed to IP week wise, Volume of dose administered will be summarized descriptively for Lead-in period and Treatment period.

Derivation for Duration of exposure is explained in section 14.1.

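### AEs and infusion reactions are summarised by period only as counts and n (%), although planned AGA BETA BS exposure is 13.5 times the Fabrazyme exposure

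*SAP*

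**What the plan says.** SAP 17.1 sets the general rule: "Adverse events collected during the trial will be summarized by treatment groups and Period based on SAF population". The metric is also given there: "The number of AE and the number and percentage of patients experiencing AE will be summarized by severity and relationship to the Fabrazyme® and AGA" (the quote stops within the test product's name). SAP 17.1.1 applies this to both periods: "An overview of AE summary will be provided for both Lead-in period and Treatment period with the No. of events and n", where n is accompanied by a percentage. One row of that overview is "Infusion Associated reactions". SAP Appendix 1 names the two output groups as Fabrazyme for the lead-in and AGA BETA BS for the treatment period. Protocol 9.2.5 uses the same metric: "Physical assessments, AEs and IARs will be summarized by frequency counts and percentage".

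Exposure in the two periods is stated in SAP 3.1. For the first: "Lead-in period: all participants will receive 2 intravenous (IV) infusions of Fabrazyme®, provided by Biosidus, at a dose of 1 mg/kg of body mass". For the second: "Participants will receive a total of 27 infusions".

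SAP 14 summarises exposure by period, including "Duration of exposure (in weeks), no. of IP administrations", but neither quantity is used as a denominator for AEs or IARs. Neither document plans a rate per infusion, a rate per patient-time or an equal-exposure view.

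**The concern.** Event counts and the percentage of patients with at least one event both rise with exposure. When one product is observed for 2 infusions and the other for 27, the second will show more events and more affected patients even if the two products carry identical risk.

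This matters because the protocol's rationale presents the trial as a comparative study of similarity in safety as well as efficacy, and the lead-in is the only Fabrazyme AE experience collected prospectively under the protocol. Anyone reading the by-period figures for a signal sees product and exposure completely confounded. An equally safe test product would look worse, and a real difference in either direction could not be recognised.

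**Working it through.** **Exposure.** The plan's 27 infusions reproduce: 54 weeks / 2 = 27, and (379 − 1)/14 = 27, with infusions on Days 1 to 365 and none at the final visit on Day 379. Lead-in infusions are on Days −28 and −14 (protocol Schedule of Activities).

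- Infusions: 27/2 = 13.5.
- Time at risk: Day −28 to Day 1 is 28 days and Day 1 to Day 379 is 378 days, so 378/28 = 13.5. Counting the lead-in from the earliest screening day (Day −42) gives 378/42 = 9.0.

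**Equal risk per infusion, independent infusions.** The documents give no per-infusion risk. Protocol 2.3.1 says only that IARs are rare or absent in patients on continued agalsidase beta. The risk p below is therefore an assumption shown over a range. The share of patients with at least one event in m infusions is 1 − (1 − p)^m, and expected events in N = 20 patients are 20 × m × p.

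| p | Patients, 2 infusions | Patients, 27 infusions | Ratio | Expected events |
|---|---|---|---|---|
| 0.5% | 1.0% | 12.7% | 12.7 | 0.2 vs 2.7 |
| 1% | 2.0% | 23.8% | 11.9 | 0.4 vs 5.4 |
| 2% | 4.0% | 42.0% | 10.6 | 0.8 vs 10.8 |
| 5% | 9.8% | 75.0% | 7.7 | 2 vs 27 |
| 10% | 19.0% | 94.2% | 5.0 | 4 vs 54 |
| 30% | 51.0% | 100.0% | 2.0 | 12 vs 162 |
| 50% | 75.0% | 100.0% | 1.3 | 20 vs 270 |

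The patient ratio exceeds 3 for p below about 18% and falls to 2 at about 29%. The event ratio is 13.5 at every p.

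**Between-patient heterogeneity.** Protocol 2.3.1 says that patients with antibodies have a higher IAR risk, so a common p is too simple. In a beta-binomial model with mean p and intra-patient correlation ρ, the share affected is 1 − B(a, b + m)/B(a, b), where a = p(1/ρ − 1) and b = (1 − p)(1/ρ − 1). The values of ρ are also assumptions.

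- p = 1%, ρ = 0.05: 1.9% vs 15.8%, ratio 8.1.
- p = 1%, ρ = 0.3: 1.7% vs 6.2%, ratio 3.7.
- p = 10%, ρ = 0.05: 18.6% vs 83.0%, ratio 4.5.
- p = 10%, ρ = 0.3: 16.3% vs 48.0%, ratio 2.9.

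Over mean p of 1% to 10% and ρ of 0.05 to 0.3, the ratio runs from 2.9 to 8.1.

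**AEs in calendar time.** With a constant rate λ per patient-year and 4 vs 54 weeks, the share affected is 1 − exp(−λ × weeks/52). For an assumed λ = 1 this gives 7.4% vs 64.6%. For λ = 5 it gives about 32% vs 99%, roughly 3-fold.

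**What a rate does.** At p = 5% and N = 20, the rates are 2/40 and 27/540, both 5.0 per 100 infusions. The ratio is 1.0.

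**Which patient-time denominator.** SAP 14.1 defines duration as last minus first administration plus 1 day. On schedule this is 15 days for the lead-in (2.1 weeks) and 365 days for treatment (52.1 weeks). Under SAP 17.1, however, an AE counts as lead-in until the first AGA BETA BS dose, so lead-in events accrue over about 28 days, and treatment events accrue over about 378. With a true rate of 1 per patient-year in both periods, dividing by the 14.1 durations gives 28/15 = 1.87 for Fabrazyme and 378/365 = 1.04 for AGA BETA BS. That is a spurious 1.8-fold excess for the reference product.

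**The case against.** The strongest case against is that no product comparison is planned. The safety objective is to characterise AGA BETA BS, and both SAP 17 and protocol 9.2.5 rule out formal safety testing. A reader might infer that the SAP intends to conclude similar safety from the overview. It does not: no section draws that conclusion from this table.

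The affected display is also narrow. The tables by system organ class and preferred term with severity and relationship, and the SAE summary, are specified for the treatment period, and SAP 17.1.5 does not describe a two-column IAR table. That the two periods appear side by side is inferred from the by-period rule and the output group labels. The table shells are separate templates that are not in the text, so their layout and footnotes are unknown.

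Finally, the exposure difference is stated openly, and events per infusion could be worked out from the overview counts and the number of administrations in SAP 14.

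These points limit the issue to a descriptive display. They do not remove it. Ruling out p-values does not stop two percentages labelled by product from being read against each other, and a rate left for the reader to construct is not a prespecified output.

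**Conclusion.** The gap is real and the improvement is cheap. AEs and IARs are planned by period and product only as counts and n (%), across a 13.5-fold exposure difference, and that metric cannot inform similarity in safety.

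Under equal per-infusion risk the event-count contrast is 13.5-fold whatever the risk. The patient-percentage contrast depends on assumptions that the documents do not settle: about 12-fold falling to 5-fold for risks of 1% to 10% with independent infusions, about 3- to 8-fold with heterogeneity between patients, and 2-fold or less for very common events.

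Two stronger readings are not supported. One is that the test product must appear 8 to 12 times worse. That needs an assumed low risk, identical in every patient and independent across infusions, whereas the protocol itself expects risk to vary with antibody status. The other is that SAP 14 already supplies both denominators. It does for infusions. For patient-time its duration would replace a distortion against AGA BETA BS with one against Fabrazyme.

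**What to change.** In SAP 17.1.1 and 17.1.5, add by period:

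- IARs per 100 infusions, using the number of administrations already summarised in SAP 14.
- AEs and SAEs per patient-year. Lead-in time should run from the first Fabrazyme infusion to the first AGA BETA BS dose, or to discontinuation if earlier. Treatment time should run from the first AGA BETA BS dose to the final or discontinuation visit. The SAP 14.1 duration should not be used.

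Present the rates descriptively, with confidence intervals that allow for repeated events within a patient, or with a note that Poisson intervals ignore clustering. Footnote the crude columns as not comparable because of unequal exposure. If AGA BETA BS infusions 1 and 2 are shown beside the 2 lead-in infusions, footnote that antihistamine pretreatment was compulsory only for the former (protocol 6.8).

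The cost is SAP wording, one or two tables and one new time-at-risk derivation, with no new data and no formal testing. The downside is that lead-in intervals will be wide: 20 patients give only 40 Fabrazyme infusions.
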